6.1 Schedule of assessments

- 6.2 Handling of unscheduled visits
- 6.3 Handling of missed visits
- 6.4 Stopping rule
- 7. Statistical methods
- 8. Regulatory and ethical issues
 - 8.1 Protocol institutional approval
 - 8.2 Informed consent
 - 8.3 Data handling, safety and quality assurance
 - 8.3.1 Source documentation
 - 8.3.2 Data safety
 - 8.3.3 Data quality assurance
 - 8.4 Good clinical practice
 - 8.5 Study duration and premature termination
- 9. Appendices
 - 9.1 Appendix A – Molecular microbiological protocol
 - 9.2 Appendix B – Application of Comprifore system
 - 9.3 Appendix C – Ankle brachial index measurement
 - 9.4 Appendix D – Itch assessments
 - 9.5 Appendix E – Insight wound imaging system
 - 9.6 Appendix F - Acticoat 7® application instructions
 - 9.7 Appendix G - Wound-QoL questionnaire
 - 9.8 Appendix H - EQ-5D-5L instrument
- 10. References

1. EXECUTIVE SUMMARY:

Sponsor: BSN Medical Inc.

Primary investigators:

[name], MAS. Assistant professor of dermatology, University of Miami, FL

[name]. Assistant professor of dermatology, University of Miami, FL

[name]. Associate Professor of Biostatistics, University of Miami, FL

Objective: The goal of the study is to investigate the effectiveness of Cutimed® Sorbact® (Study Device) in modifying bacterial load in venous leg ulcers (VLU).

Design: This is an exploratory study in a single center, observer masked, active control, randomized trial.

Overall, 45 subjects with VLU who have persistent wounds and have been previously treated with silver based therapy will be 1:1 randomized to receive up to four applications over up to four weeks of Study Device or Comparator (silver impregnated contact layer dressing - Acticoat®) with 2 weeks follow up period.

Outcomes: Primary outcome is the change in bacterial load compared to baseline.

Secondary outcomes: Bacterial silver resistance based on genetic and phenotypic characterization over time (see appendix A for molecular microbiology protocol), healing rate, complete healing at 6 weeks, pain, quality of life (QOL) measurements and adverse events.

1.1 Table of assessments and study calendar:

Phase	Screening		Treatment					Follow up	
	-2	-1	0		+1	+2	+3	+4	
Week	S1	S2	T0 (pre random)	T0(post random)	T1	T2	T3	T4	F1
Visit		±2	±2		±2	±2	±2	±2	±2
Window (days)									
Informed consent	X								
Eligibility	X	X	X						
Demographics	X								
Medical history	X								
Concomitant medication	X	X	X		X	X	X	X	X
Study ulcer history									
Physical exam (focused)	X								X
Vital signs	X								X
Pain (VAS)	X	X	X		X	X	X	X	X
Wound area	X	X	X		X	X	X	X	X
Product application				X	X	X	X		
Tissue collection			X			X	X		
QOL				X				X	X
Randomization				X					
Sharp debridement	X	X		X	X	X	X	X	
Wound photography	X	X		X	X	X	X	X	X
Compression	X	X		X	X	X	X	X	X
Adverse events	X	X	X		X	X	X	X	X
ABI	X								
Venous Doppler	X								
Fitting for stocking								X	X

Table 1. Table of assessments and study calendar

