4.1 Overview

Subjects for the study will be recruited from the University of Miami (UM) patient population as well as other patients referred to UM for the study. The recruitment goal for this pilot study is 30 subjects. Considering up to 15% drop out rate, the study will enroll up to 35 subjects with the goal of having 15 subjects in each arm complete the study.

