4.5 Subject withdrawal

A subject randomized into a treatment arm that has not completed the study as defined by section 4.4 will be considered incomplete.

Any subject is free to withdraw from the study without explanation and without future consequence on future care. Investigator will make every effort to obtain reason for withdrawal of subject especially eliciting any adverse event.

The PI may suspend or terminate a subject from the trial if deemed medically necessary. The reasons for suspension or termination will be recorded in the patient's study documents.

5. Study procedures

5.1 Subject identification:

After signing informed consent the subject will be assigned a subject ID number beginning with BSN2018001, BSN2018002 and so on. All study related materials (e.g. source documents, investigational device etc.) will be labeled with the subject ID a priori.

5.2 Randomization and sequence allocation:

A random sequence of numbers from 1-16 will be generated in two columns (A= Cutimed® Sorbact® and B= Acticoat®) in Excel (Microsoft, Redmond, WA). 8 envelopes with a card labeled Cutimed® Sorbact® and 8 with a card labeled Acticoat® will be created, sealed and assigned the random numbers a priori before randomization of the first subject BSN2018001 by two people who are not part of the research team. Envelopes will be placed in secure location in number order. This procedure will generate a random sequence of 16 subjects and 8 subjects in each arm. This procedure will be repeated for another block of subjects 17-30, and 31-36. The block of 31-36 will only be used if the total randomization does not reach to n=30. Once a subject is randomized, the investigator will open the next envelope in the sequence and write the subject number on the card and include it as part of the record in the source documents. This will be the treatment assignment for the rest of the study.

5.3 Blinding:

Due to the nature of the study and products, investigator blinding is unrealistic and subject blinding is unlikely. Research staff will avoid naming the dressing or suggesting the assignment to the subjects. However, an independent monitor with experience in treating wounds will be blinded to the treatment assignment and will confirm healing outcomes based on images. [name] and laboratory personnel will be blinded to the treatment assignments as well. Unblinding will occur when the study is officially closed for statistical analysis at <https://clinicaltrials.gov/>.

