6.3 Handling missed visits

It is preferred that subjects are seen at regular intervals. However, this may not be possible at times. If a subject needs to miss a visit, every effort should be made to reschedule as close as possible to the original date and then resume following visits at the original intervals. For example, if a subject regularly visits on Wednesdays and will miss a visit and a makeup visit is scheduled for that Friday, the next visit should return to the original intervals and be scheduled for the next Wednesday.

6.4 Stopping rule:

The PI may decide to stop the trial due to safety concerns at any time during the trial. The PI may consult the local Institutional Review Board (IRB) and/or Sponsor for safety related decisions.

7 Statistical methods

This study is a single center randomized longitudinal pilot study to investigate the effectiveness of Cutimed® Sorbact® (Study Device) compared to Comparator (silver impregnated contact layer dressing - Acticoat®) in modifying bacterial load in venous leg ulcers (VLU). Efficacy will be measured as the difference in change in bacterial load compared to baseline between two study arms i.e. Study Device vs. Comparator. This study will also

compare bacterial silver resistance based on genetic and phenotypic characterization over time, healing rate, complete healing at 6 weeks, pain, quality of life (QOL) measurements and adverse events as secondary endpoints.

We expect to study n=30 subjects for both the primary and secondary endpoints. The number of subjects estimated for the study (n=30) is not based on hypothesis driven statistical power calculation. Rather, as a pilot study, a goal for this investigation is to generate effect estimates that will assist in determining an appropriate sample size for future studies.

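### The executive summary randomises 45 subjects, but the rest of the plan supports 30 completers with 35 or 36 randomised, and read literally the release rule for the reserve envelopes leaves dropout uncovered

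*Combined protocol and SAP*

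**What the plan says.** Five places give a number of subjects.

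- **Section 1, Executive summary, Design:** "Overall, 45 subjects with VLU who have persistent wounds and have been previously treated with silver based therapy will be 1:1 randomized".
- **Section 4.1:** "The recruitment goal for this pilot study is 30 subjects". Then, allowing for dropout of up to 15%, "the study will enroll up to 35 subjects with the goal of having 15 subjects in each arm complete the study".
- **Section 5.2:** a first block of 16 envelopes, 8 per arm, and then "This procedure will be repeated for another block of subjects 17-30, and 31-36".
- **Section 7:** "We expect to study n=30 subjects for both the primary and secondary endpoints". The same section says that this number "is not based on hypothesis driven statistical power calculation".
- **Appendix A, Design:** 30 patients, 15 per arm.

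Section 5.2 also governs how the envelopes are used. Order of use: "Once a subject is randomized, the investigator will open the next envelope in the sequence". Reserve block: "The block of 31-36 will only be used if the total randomization does not reach to n=30".

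**The concern.** The number to be randomised is a basic design figure, and the summary contradicts the body on it. The sentence in the summary is about subjects who are randomised, so 45 cannot be a screening figure. A site working from the summary would run out of envelopes before reaching 45.

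The second issue is the reserve. Section 4.1 plans for dropout and wants 15 completers per arm, and block 31-36 looks like the means of providing for it. If the release condition blocks that use, randomisation ends at 15 per arm and a single dropout after randomisation puts the goal out of reach. Staff would then have to fall short of the goal or depart from the written rule.

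**Working it through.** **1. The plan's own figure of 35.** Inputs from Section 4.1: 30 completers, dropout up to 15%.

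- Dividing by the retention rate: 30 / (1 − 0.15) = 35.3, rounded up to 36.
- Adding 15%: 30 × 1.15 = 34.5, rounded up to 35.

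The stated 35 is therefore reproduced, and 36 is the next even number.

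**2. Envelopes (Section 5.2).** 16 + 14 + 6 = 36, that is 18 per arm.

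**3. Testing 45 against these inputs.**

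- Envelope shortfall: 45 − 36 = 9.
- Dropout implied if 45 are randomised to obtain 30 completers: 1 − 30/45 = 33%, against the stated maximum of 15%.
- Expected completers from 45 at 15% dropout: 45 × 0.85 = 38.25, against a goal of 30.
- 45 is odd, so it cannot be divided equally 1:1.

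**4. The release condition.** Let r be the number already randomised. Envelopes are opened in order, so the next one is r + 1. Needing envelope 31 or later means r ≥ 30, while the condition requires r < 30. No value of r satisfies both. On this literal reading, and with no spoiled envelopes, randomisation ends at 30, split 15/15.

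**5. What that does to the goal of 15 completers per arm.** Let d be the dropout rate after randomisation, assumed independent between subjects and equal in the two arms. The 15% is the plan's upper limit; 5% and 10% are assumed to show a range.

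- 30 randomised: all must complete, so the probability is (1 − d)^30.
- 35 randomised (18/17): P(Bin(18, 1 − d) ≥ 15) × P(Bin(17, 1 − d) ≥ 15). At d = 0.15 this is 0.720 × 0.520 = 0.374.
- 36 randomised (18/18): P(Bin(18, 1 − d) ≥ 15)². At d = 0.15 this is 0.720² = 0.519.

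| Randomised, regardless of dropout | d = 5% | d = 10% | d = 15% |
|---|---|---|---|
| 30 (15/15) | 21% | 4% | 0.8% |
| 35 (18/17) | 94% | 69% | 37% |
| 36 (18/18) | 98% | 81% | 52% |

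At 15% dropout the expected number of completers is 30 × 0.85 = 25.5, 35 × 0.85 = 29.75 and 36 × 0.85 = 30.6 respectively.

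**The case against.** **That 30, 35 and 36 also contradict one another.** A reader might infer this from the list of figures. The documents do not support it. Section 4.1 links 30 to 35 through the dropout allowance, and step 1 reproduces that link. Thirty-six envelopes are a supply with equal arms, and one spare does not contradict a cap of 35. Section 7's 30 can be read as the number analysed. What remains is loose labelling: Section 4.1 calls 30 a recruitment goal, and Appendix A says that 30 will be enrolled.

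**That the reserve block can never be used.** This too is tempting, but too firm. Section 5.1 assigns subject numbers at consent, and Section 5.2 describes the blocks as blocks of subjects. If 31-36 are subject numbers and screen failures use some of them up, those numbers would be needed exactly when fewer than 30 have been randomised, and the rule would work. The text favours the other reading. The random numbers are attached to envelopes, the next envelope is opened in turn, and the subject's number is written on the card afterwards, so envelope order does not depend on the consent number. Even on the subject-number reading, the reserve would make good losses in screening and bring the randomised total up to 30; it would not replace subjects lost after randomisation.

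**That the trial loses power.** It has none to lose: Section 7 says that n=30 does not come from a power calculation, and 15 per arm is a goal. The 0.8% is simply the chance of no dropout at all, and it should not be read as a failure probability for the study.

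**Conclusion.** The 45 is wrong as it stands. It conflicts with Sections 4.1, 5.2 and 7 and Appendix A, no passage reconciles it, and it exceeds the envelope supply by 9. This conclusion rests on the text and simple arithmetic alone.

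The envelope rule is a secondary point held with less certainty. On the better-supported reading the reserve cannot cover dropout, and the goal of 15 completers per arm is met only if nobody drops out: 0.8% at the stated 15%, and 21% and 4% at the assumed 5% and 10%. These figures assume independent dropout, equal in both arms, occurring after randomisation. Losses during screening use no envelope and do not have this effect.

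The consequence is limited to conduct and to the precision of pilot estimates. It should be corrected because the correction is cheap and the figure governs how many people are randomised.

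**What to change.** 1. Replace 45 in the executive summary with one maximum number randomised, confirmed by the sponsor. The rest of the document supports 35 or 36.
2. Use the same maximum in Sections 4.1 and 5.2, so that the cap and the envelope count agree.
3. State in Section 7 and Appendix A that 30 is the completer or analysis target.
4. Reword the Section 5.2 condition so that the reserve can be used. The preferred rule is to randomise to the stated maximum regardless of dropout. Describe 15 per arm as a target, since at 15% dropout it is still met only 37% (35) or 52% (36) of the time.

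The alternative is to open reserve envelopes only as subjects fail to complete. That makes further randomisation depend on non-completion, when the investigator is unblinded (Section 5.3.1) and may terminate a subject's participation (Section 4.5). It also waits on outcomes that may be known only up to six weeks after the 30th randomisation (four weeks of treatment plus two of follow-up).

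Cost: a text amendment, with consent form revision if the IRB requires it (Section 8.2). Five or six subjects beyond 30 would be randomised, which the plan already provides for; choosing 36 goes one above the stated cap of 35. If the sponsor does intend 45, nine more envelopes are needed and the figures in the other sections must change to match.

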2. BACKGROUND

Wounds are the most common and costly skin disease. Chronic wounds are wounds that fail to progress through the normal process of healing. Briefly, normal healing occurs in four phases that overlap significantly [1]. Immediately following injury damage to endothelial cells exposes collagen and activates platelets to form a plug thus initiating the hemostasis phase. Chemotactic signals from leukocytes and platelets attract immune cells to the wound and activate fibroblasts, smooth muscle cell and endothelial cells. Minutes following injury the first neutrophils arrive to the wound site and help recruit macrophages and together degrade and clear damaged tissue and bacteria. Cytokines and growth factors secreted by macrophages in the wound result in formation of granulation tissue, fibroblast recruitment and keratinocyte migration. Within the first 24 hours growth factors secreted in the wound result in fibroblast activation that begins break down of early fibrin matrix by matrix metalloproteinases, and deposition of new extracellular matrix of collagen, elastin and other extracellular proteins assisting in scar formation and epithelialization. In the weeks and months that follow, fibroblasts transform into myofibroblasts and assist in scar contraction. The predominance of collagen 3 in the scar is slowly replaced by collagen 1 and a final scar is formed estimated to achieve about 80% of the tensile strength of unwounded skin. When a wound fails to progress through these stages of healing it is considered a chronic wound and venous leg ulcers (VLU) represent a specific case of chronic ulcers occurring on the legs. Chronic venous insufficiency and the resulting venous hypertension are typically a result of reflux or outflow failure often due to obstruction. Valvular defects, ineffective calf muscle pump function, deep vein thrombosis and its complications or arteriovenous shunting are the main causes for venous hypertension [2, 3]. The exact pathophysiology of VLU remains unclear. Current hypotheses include the fibrin cuff hypothesis and its extensions of “trap theory” with or without inflammatory cell and cytokine and/or metalloproteinases dysregulation including impaired re-epithelialization however, more research is needed to better clarify the exact mechanisms involved [2, 3].

Venous leg ulcers, the problem: Leg ulcers are very common and affect about 1-2% of the American population [2]. Venous leg ulcers (VLU) are wounds that occur in the gaiter area in the setting of chronic venous insufficiency (CVI). VLU account for about 70% of the all chronic leg ulcers and about 20% of all leg ulcers are likely a result on mixed arterial and venous disease. VLU significantly impacts patients' quality of life [4] and people with VLU are often chronically ill with significantly more comorbid conditions compared to controls [5]. VLU represent an increasingly devastating economical burden. For example, the estimated cost of treating single non healing VLU in 1987 was \$10,000 and by 2014 has ballooned to \$34,000 [6]. This is also reflected by the 5-fold increase in total cost of VLU treatment from estimated \$3 billion to \$15 billion over a similar period. The prevalence of VLU is difficult to assess yet recent estimates suggest a significant rise from 0.3% 20 years ago to more recent estimates of 0.6% in adults under 65 years of age and 2.2% in adults over 65 . Considering the aging of the population a concerning picture emerges: more ulcers occurring in sicker patients which are ever more expensive to treat. Standard care for VLU centers around edema reduction via compression and/or leg elevation, meticulous local wound care, control of infection and pain and prevention of recurrence [7]. Advanced therapies include highly absorbent dressing, matrix based

devices with and without cells and negative pressure wound therapy among others. However even with best therapies available up to 50% of VLU fail to heal [8].

Infections play a significant role in the chronicity of VLU. The high wound bacterial burden ($>10^5$ organisms per gram of tissue), even without the classic signs of infection, is also detrimental to healing [9, 10].

Silver resistance: Silver (Ag) coated dressings are increasingly being used for chronic wounds based on bactericidal properties of released Ag, despite the lack of evidence to support their use [11]. Concerns of widespread Ag resistance in bacterial isolates from chronic wounds have been raised due to the increased utilization of silver based wound dressings [12] [13]. Silver resistant-strains have also been isolated from silver-treated patients at burn centers, where these stains have sometimes caused outbreaks [14]. Furthermore our *in vivo* studies utilizing porcine wound model have shown that silver treatment induces expression of virulence genes important for biofilm formation in clinical isolates of methicillin resistant *Staphylococcus aureus* and *Acinetobacter baumannii* [15]. Although the molecular basis for silver-resistance has been previously characterized [16] [14], to date, expression of silver resistance genes as a response to therapy has not been analyzed in clinical settings.

Here we propose to analyze the presence of silver resistance on genotypic and phenotypic level in response to treatment with Study Device (Cutimed® Sorbact®) and active control (Acticoat®).

The promise of DACC technology. Dialkylcarbamoyl chloride (DACC)- coated dressings are a recent addition to wound care armamentarium. This innovative antimicrobial technology can be imbedded into various dressing and wound care products. Key to its mechanism of action, DACC, a fatty acid derivative is highly hydrophobic. On the other hand the microorganisms, commonly responsible for colonizing chronic VLU, generally have hydrophobic extracellular surfaces, and will therefore irreversibly adhere to the DACC based dressings [17]. Subsequent dressing changes result in the physical removal of large numbers of bacteria and a decreased microbial load. Since the mechanism of antibacterial action is physical binding followed by removal, there is no risk of bacteria developing resistance [17]. Developing non-silver based wound therapies is important due to reports of silver based toxicity [18]. Additionally, this may prove important as evidence exists for the onset of silver resistance in various, clinically relevant microbes [19]. This may be due to possible overuse of silver-based wound care products and is mediated by plasmid acquisition and other genetic mechanisms highlighting the need to better characterize these mechanisms in VLU [18]. Furthermore, silver and other bactericidal agents result in bacterial lysis at the wound bed leading to endotoxin release to the wound bed as well as other proinflammatory mediators that may drive the prolonged inflammatory state of VLU which has been suggested as a mechanism for the chronicity of these wounds [20]. DACC based dressing results in physical removal of whole bacteria avoiding lysis and the subsequent deleterious effects on the wound. Previous pilot studies utilizing standard microbiology culture based methods have shown efficacy of DACC based dressing (Cutimed® Sorbact®) in reducing bacterial load of VLU when compared to silver based wound dressing [19]. However,

these data are likely underestimating the scope of the problem as only 1-2% of bacterial species can be cultured using culture based methods.

In this study we use advanced molecular and microbiome methods to confirm DACC efficiency in patients with VLUs to help bridge this gap in knowledge. In addition, this exploratory study will add to existing knowledge about silver resistance in VLU and evaluate the effects of DACC treatment on VLU predisposed to be colonized with silver-resistant bacteria.

CONFIDENTIAL

3. STUDY DESIGN

3.1 Overview:

This is an exploratory, single center, observer masked, active control, 1:1 randomized clinical trial. The goal is to compare the effectiveness of Study Device (Cutimed® Sorbact® wound contact layer) to an active control (silver contact layer Acticoat®). Both devices are already approved and indicated for treatment of wounds. Standard care selected for use in this trial includes sharp debridement and compression with Jobst Comprifore® 4 layer compression system.

The study consists of three phases: two weeks screening phase (phase-1), up to four weeks treatment phase (phase-2), and two weeks follow up phase (phase-3).

In the screening phase i.e. phase-1, the Investigators will choose Study Ulcer, make baseline measurements and assessments and verify inclusion and exclusion criteria are met. Standard care will be applied without use of Study Device or active control.

The treatment phase i.e. phase-2 may last up to four weeks (if healing did not occur prior) and includes application of study dressings as well as application of standard care and measurements of primary and secondary outcomes. This will be achieved by tissue collection procedures conducted at visits T0, T2, and T3. [name] and her research team will conduct the molecular microbiology and standard microbiology assessments of the specimens collected in this study. Gene expression (by qPCR) and standard microbiology will be utilized to characterize the mechanisms through which Cutimed® Sorbact® changes the bacterial load and promotes healing of chronic venous leg ulcers. Understanding the mechanism through which Cutimed® Sorbact® stimulates healing in patients may promote, improve and expand its clinical use.

In the two weeks follow up phase i.e. phase-3 subjects will return for one visit and secondary outcomes will be assessed and standard care provided. The subjects will then be discharged from the study and return to their wound care provider for further management as indicated.

3.2 Study outcomes:

